### Sample size

The sample size calculation was made using the Edland method, R package longpower 1.0-

11, based on the following data: 8% points as smallest clinically important difference in SPADI , 15% of estimated drop-out (as mean of dropout rates from previous studies ) and 30% for adjustment

for non-linearity of the data (since there is usually a higher decrease in SPADI in the first 3 months compared to 6 months). Considering a mixed regression model for repeated measures and using a moderate effect size (corresponding to 8% as smallest clinically relevant difference), confidence level at 5%, and power at 90%, the required total sample size is **54 subjects**, taking into account 15% dropout rate. The variance of the residuals cannot be estimated from previous studies, but it has a very limited effect on the sample size. It does not change the result of the power calculation, and therefore it is not included in this analysis.

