# WP3: Data analysis

Statistical analyses will be performed using JMP ®Pro 14.0.0 (SAS Institute Inc., Cary, NC, USA) . Level of significance is set at p= 0.05. Appropriate descriptive statistics will be performed.

**OBJECTIVE 1,2,3:** A mixed regression model for repeated measures will be used to assess both the evolution of SPADI (pain and function), strength, ROM and US parameters within persons from baseline (T0) over time (T1, T2, T3) and the differences in evolution between subjects. Potential confounders are: age, gender, BMI, previous corticosteroid injections, severity of initial symptoms. They will be measured during the history taking at the first assessment and added into the mixed regression model as co-variants. If for a certain variable the percentage of missingness will be more than 15%, multiple imputation for missed observation will be used. There are three assumptions for the mixed regression model: change over time, a sensible measure for time (multiple time points of measure), normality of residuals (it will be checked using a Shapiro-Wilk test). If these residuals are not normally distributed, an appropriate transformation will be performed first. Therefore, this model best fits the longitudinal design of the RCT. **OBJECTIVE 4**: correlation analysis between tendon structures and clinical symptoms using the correlation for pairs of continuous variables in JMP.

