### WP2: RCT

The RCT started in July 2020 and is still on going. In the initial FWO application the aim was to start the recruitment in April 2020 and to complete it by April 2021, with the final follow up in October 2021 (6 month after baseline assessment). A change to the timeline and sample size was necessary because of the low recruitment rate during the pandemic of Covid-19. The recruitment rate during the feasibility study before the pandemic (November 2019-February 2020) was 4-5 patients/month. The recruitment rate during the RCT was: 2.6 patients/month during the first year (July 2020-July 2021) and then 1.2 patient/month in the following 6 months (August 2021-January 2022). Fifty-four patients were included in the initial sample size calculation, estimating 15% of drop-out, power=90% and minimal clinically important difference (MCID)=8 points on the primary outcome SPADI. We planned to recruit patients until May 2022, aiming to 44 patients, with the last follow up measure in November 2022. Forty-four patients will still allow to have a well-powered study (85%) with MCID=10 points, which is considered in the range 8-13 points of the MCID in SPADI (Roy JS, MacDermid JC, Woodhouse LJ. Measuring shoulder function: a systematic review of four questionnaires. Arthritis Rheum. 2009;61(5):623-32). The extended time for data analysis in 2023 will allow the PhD student to conduct a thorough data analysis of objective and subjective data (see "Data analysis for 2nd term"). Status: 42 patients were recruited by the end of April 2022.

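### The moderate effect, 54 patients and 90% power in the sample-size section do not fit together under its own method, and neither 90% nor the renewal's 85% is supported by stated inputs

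*Combined protocol and SAP*

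**What the plan says.** The Sample size section (WP2: Randomized controlled trial) names the Edland method in the R package longpower. It takes "8% points as smallest clinically important difference in SPADI" as the target, with 15% dropout and a 30% adjustment for non-linearity. It then reports, "using a moderate effect size (corresponding to 8% as smallest clinically relevant difference), confidence level at 5%, and power at 90%, the required total sample", which comes to 54 with dropout included. No numerical standardised effect, SPADI SD, slope variance or within-patient correlation is given. On residual variance it says "The variance of the residuals cannot be estimated from previous studies, but it has a very limited effect on the sample size", and then "It does not change the result of the power calculation, and therefore it is not included in this analysis".

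The renewal of 11/5/2022 (WP2: RCT) lowers the recruitment target because of slow accrual and says "Forty-four patients will still allow to have a well-powered study (85%) with MCID=10 points". It gives no SD either.

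The analysis section (WP3: Data analysis) plans a mixed model over T0, T1, T2 and T3 with initial severity among the covariates, and says "Level of significance is set at p= 0.05". Neither section says whether the test is one-sided or two-sided.

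**The concern.** One sentence ties together an effect size described as moderate, a sample size and a power. Under the method the section names, with the simplification it makes, any two of these fix the third, so they can be checked against each other, and they disagree. The section also dismisses the one variance component it mentions, and the renewal offers a second calculation with no inputs.

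SPADI is the primary outcome, and the renewal describes the reduced trial as well powered. A reader who accepts 85% to 90% power may give a non-significant SPADI result more weight against a worthwhile difference than the design has been shown to carry.

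**Working it through.** **Inputs from the documents.** N = 54, 5% level, 90% power, 8 points, 15% dropout, 30% adjustment (Sample size); visits at 0, 6, 12 and 26 weeks (Design); N = 44, 85%, 10 points (renewal, WP2: RCT).

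**Assumptions.** Two-sided test, 1:1 allocation, normal approximation. Dropout multiplies N by 0.85. The 30%, whose use is not explained, is taken to divide N by 1.3 where it is applied. Moderate is taken as 0.5, the conventional value.

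**1. Reproducing 54.** This cannot be done, because no variance is stated. Edland's formula is

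n per arm = 2(z_α + z_β)² × (slope variance + residual variance/Sxx) / Δ².

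With residual variance set to zero it becomes the two-group formula in slope-SD units, and total N = 4(1.960 + 1.282)²/d². At d = 0.5 that gives 168, or 168/0.85 = 198 with dropout, or 198 × 1.3 = 257 with the 30% as well. None is near 54.

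**2. Working back from 54.** The detectable effect is d = 2(1.960 + 1.282)/√N, and power = Φ(d√N/2 − 1.960).

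| Effective N | d for 90% | Power at 0.5 | Power at 0.8 |
|---|---|---|---|
| 54 | 0.88 | 45% | 84% |
| 54 × 0.85 = 45.9 | 0.96 | 40% | 77% |
| 45.9/1.3 = 35.3 | 1.09 | 32% | 66% |

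Even 0.8, conventionally large, does not reach 90%.

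**3. Residual variance.** The visit times have mean 11 weeks, so Sxx = 121 + 25 + 1 + 225 = 372. In units of the 26-week period this is 372/26² = 0.550. Take Δ = 8 points over 26 weeks and a slope SD of 8.4, the value that roughly returns 54 when residual variance is zero. The residual SDs below are illustrative.

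| Residual SD | Slope variance + residual variance/0.550 | n per arm | Total/0.85 |
|---|---|---|---|
| 0 | 70.6 | 23.2 | 55 |
| 5 | 116.0 | 38.1 | 90 |
| 10 | 252.3 | 82.8 | 195 |

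Any residual variance above zero raises N.

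**4. The two calculations against each other.** Both are put on the same formula with the same 15% dropout.
- 54, 90%, 8 points: SD = 8/0.957 = 8.4.
- 44, 85%, 10 points: N = 44 × 0.85 = 37.4 and d = 2(1.960 + 1.036)/√37.4 = 0.980, so SD = 10/0.980 = 10.2.
- With SD 8.4, 44 patients would have about 96% power at 10 points, not 85%.
- With SD 10.2, 54 patients would have about 76% power at 8 points, not 90%.

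The SD here is the total spread used in the slope comparison, so this check needs no reading of moderate and no split between slope and residual variance. It does need both calculations to treat dropout and the 30% alike. If the 30% entered only the second, its SD would be 10/1.117 = 8.95, which narrows the gap to 8.4 without closing it.

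**5. Raw SPADI scale under the planned type of model.** Assume 8 points = 0.5 SD (SD 16), equal correlation ρ between visits, and baseline adjustment. The variance factor is 1 − ρ² at one visit and (1 + 2ρ)/3 − ρ² for the mean of three visits.

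| ρ | 8 points, 45.9 evaluable: one visit / mean of three | 10 points, 37.4 evaluable: one visit / mean of three |
|---|---|---|
| 0.3 | 43% / 72% | 52% / 82% |
| 0.5 | 50% / 75% | 60% / 84% |
| 0.7 | 66% / 86% | 76% / 93% |
| 0.8 | 81% / 94% | 89% / 98% |

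Power is therefore anywhere from about 43% to 94% at 8 points, depending on quantities that the plan does not give.

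**The case against.** The strongest reply is that the target is defined in points and that *moderate* is a loose adjective. Without it, the sentence holds no contradiction, only a missing variance. That is largely right for the first fault, and it is why the fix asks for the inputs. But the adjective is printed as the effect size used, and no reading of it up to 0.8 rescues 90%. The residual-variance and consistency faults do not touch the adjective at all.

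A second reply is that the trial will be analysed with a baseline-adjusted mixed model over three follow-up visits, which can be far more efficient than a bare two-group comparison. This also stands. A reader might infer from step 2 that the trial has only about 30% to 45% power. The documents do not support that as a statement about the trial: it needs a moderate effect of exactly 0.5, measured in slope SDs, and a two-sided test. One-sided, power at 0.5 would be 44% to 58%, and the effect detectable with 90% power 0.80 to 0.98, still not moderate. On the raw SPADI scale, step 5 runs much higher for the three-visit mean. That mean is not the slope test that was used to size the trial, however, so it does not validate the printed 90%.

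Third, the renewal never calls its effect moderate; it claims 85% for 10 points. It would be wrong to read it as promising 85% for a moderate effect. Finally, nothing in the documents says that non-significance will be taken as no difference. The hypothesis is superiority and the stated aim is proof of concept. The risk lies in how readers may use the power claim, not in a planned misreading.

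**Conclusion.** The point holds in three parts.

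- Under the section's own method, 54 patients at 90% power corresponds to 0.88, 0.96 or 1.09 slope SD according to how dropout and the 30% are treated. That is not moderate. If moderate means 0.5 slope SD, power is about 32% to 45%. This rests on a two-sided test, 1:1 allocation and zero residual variance.
- The statement that residual variance leaves the result unchanged is wrong for this formula. Only the size of the effect (55, 90 or 195 patients) is illustrative.
- The two stated calculations imply different SDs, about 8.4 and 10.2, if dropout and the 30% enter both in the same way.

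The 90% and 85% are therefore unsupported; they are not shown to be some specific lower value. A reader might also infer that a null result could not exclude a moderate effect. That is conditional too. On the slope-SD scale with 54 enrolled, the 95% interval half-width is 0.53 to 0.66, so 0.5 would remain possible at an estimate of zero. For a baseline-adjusted mean of three visits with 45.9 evaluable and ρ = 0.5, it is about 0.37 raw SD, which would exclude 0.5 at an estimate of zero.

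**What to change.** In the Sample size section delete *moderate*, and in the renewal delete *well-powered*. Recompute power for both 8 and 10 points at the actual target of 44 enrolled (about 37 completing), from a single stated set of inputs:

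- the SPADI SD or slope variance, with its source;
- a residual variance above zero, or a within-patient correlation, shown as a range;
- the contrast tested (slope, one visit, or mean of visits), matching the primary analysis;
- the sidedness of the test;
- how the 30% enters, applied the same way throughout.

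Print the resulting power, or the detectable difference in points, in place of 90% and 85%. The back-calculated values above should not be inserted as if they had been design inputs. In the report, judge SPADI by the estimated difference and its 95% interval against 8 to 10 points, not by non-significance.

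The cost is one recalculation and some rewording. No extra patients are needed. The downside is a stated power that will probably look less favourable.

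### The two stated powers (54 patients, 90%, 8 points; 44 patients, 85%, 10 points) cannot share one variance and one set of adjustments, and no variance is stated for either

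*Combined protocol and SAP*

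**What the plan says.** The Sample size section (WP2: Randomized controlled trial) names the Edland method and a mixed regression model for repeated measures. It sets the calculation out as "using a moderate effect size (corresponding to 8% as smallest clinically relevant difference), confidence level at 5%, and power at 90" per cent, and arrives at 54 patients with 15% dropout included. A further 30% is assigned to an adjustment "for non-linearity of the data (since there is usually a higher decrease in SPADI in the first 3 months compared to 6 months"; how it enters the calculation is not described. On variance the section says "The variance of the residuals cannot be estimated from previous studies, but it has a very limited effect on the sample size", and then "It does not change the result of the power calculation, and therefore it is not included in this analysis". The effect size is called moderate, without a number.

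The renewal outline (WP2: RCT) restates the first target: "Fifty-four patients were included in the initial sample size calculation, estimating 15% of drop-out, power=90" per cent, at 8 points. It gives the reason for the reduction, "A change to the timeline and sample size was necessary because of the low recruitment rate during the pandemic of Covid-19", and the new basis, "Forty-four patients will still allow to have a well-powered study (85%) with MCID=10 points". It notes that 10 lies within a published range of 8 to 13 points. The level, dropout, 30% adjustment and variance behind the 85% are not restated. At that date "42 patients were recruited by the end of April 2022".

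WP3: Data analysis names the mixed model and the 0.05 level, but no variance.

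**The concern.** The Sample size section says that a variance component cannot be estimated and, in the next sentence, that it makes no difference to the power. The second statement needs at least a plausible range for the first, and none is shown.

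Both targets also lack the one input from which power could be checked. Set side by side, they do not look like one calculation. Going from 54 to 44 patients costs some power, but raising the difference from 8 to 10 points gains more, so power should have risen. The stated figure falls from 90% to 85%.

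The 85% is the assurance offered that 44 patients are enough after recruitment fell short. If that figure rests on a larger variance than the first one did, power at 8 points, which the Sample size section treats as the smallest clinically important difference, is well below what a reader would suppose.

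**Working it through.** **Inputs.** From Sample size: N = 54 including 15% dropout, difference 8, level 5%, power 90%, a 30% adjustment. From the renewal outline, WP2: RCT: N = 44, difference 10, power 85%, 42 recruited. Assumed because not stated: two-sided test, 1:1 allocation, normal approximation.

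**1. The plan's own figures.** Neither the 54 nor the 85% can be reproduced directly, because the variance is missing. The variance that each implies can only be solved for and compared.

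**2. Implied variance.** With common handling of dropout and of the 30%, the variance is proportional to C = N × δ² / (z_α + z_β)², and the constant cancels in the ratio.

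- 54 / 90% / 8: (1.960 + 1.282)² = 10.507; C = 54 × 64 / 10.507 = 328.9
- 44 / 85% / 10: (1.960 + 1.036)² = 8.978; C = 44 × 100 / 8.978 = 490.1

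The ratio is 490.1 / 328.9 = 1.49. It is 1.52 if one-sided, and 1.47 with the noncentral t distribution.

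**3. Power under each.** Power = Φ(√(N × δ² / C) − 1.960). For 44 patients at 10 points under the first variance: √(4400 / 328.9) = 3.657; 3.657 − 1.960 = 1.697; Φ = 95.5%.

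| Patients, difference | Variance of first calculation | Variance of second calculation |
|---|---|---|
| 54, 8 points | 90% (stated) | 75.7% |
| 44, 10 points | 95.5% | 85% (stated) |
| 44, 8 points | 83.3% | 66.9% |
| 42, 10 points | 94.7% | 83.3% |
| 42, 8 points | 81.6% | 64.9% |

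The 95.5% becomes 95.3% with the noncentral t and 95.1% one-sided. Under the first variance, 85% power at 10 points would need 328.9 × 8.978 / 100 = 29.5, so about 30 patients.

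**4. The same on the SD scale.** V = n × δ² / (2 × (z_α + z_β)²), with n evaluable patients per arm after 15% dropout.

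- n = 54 × 0.85 / 2 = 22.95: V = 22.95 × 64 / (2 × 10.507) = 69.9, SD 8.4
- n = 44 × 0.85 / 2 = 18.7: V = 18.7 × 100 / (2 × 8.978) = 104.1, SD 10.2

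These SDs ignore the 30% adjustment. If it was applied to N, they are 7.3 and 9.0 (N × 1.3) or 7.0 and 8.5 (N / 0.7). The ratio stays 1.49. They come from a two-means formula, so they describe the effective variance and do not estimate any term of the mixed model.

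**5. Could different handling explain it?** The effective size of the 44 would have to be cut by 1 − 1/1.49 = 33% more than that of the 54. Keep 15% dropout in the 54, as stated, and allow 15% or none in the 44. Let the 30% be absent, N × 1.3, N / 0.7, effect × 0.7 or effect / 1.3 in each calculation. That makes 5 × 10 = 50 combinations. Four bring the 44 within two points of 85% (83.1%, 86.3%, 86.4%, 86.4%). Two of them leave the 30% out of the 54, contrary to the Sample size section. The other two apply it to N in the first calculation and to the effect in the second.

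**6. The omitted residual term.** Assume that the calculation compares slopes. The variance of one patient's estimated slope is σ_s² + σ_e² / S, where S is the sum of squares of visit times about their mean. For weeks 0, 6, 12 and 26 the mean is 11 and S = 121 + 25 + 1 + 225 = 372. The second term cannot be negative, so setting it to zero cannot understate power. Over a horizon of H weeks its weight is H² / S: 676 / 372 = 1.82 at 26 weeks, or 144 / 372 = 0.39 at 12 weeks. Neither σ_e nor the horizon of the 8 points is given, so the loss of power cannot be sized.

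**The case against.** The strongest reply is that no sum in the documents is shown to be false. The 54-patient figure is labelled as the initial calculation and the 44-patient target replaces it. The 1.49 is a contradiction only if the variance, model and adjustments were the same both times, which the renewal outline does not claim. A variance revised in the interval would remove the conflict. This stands, and it limits the point to figures that are not reconcilable as documented. It does not dispose of it: the renewal outline repeats 54 patients, 90% and 8 points as its comparator and mentions no new variance or handling.

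On the residual term, the slope reading is an assumption. An SD of change, if that was what was entered, would already contain part of the term, and the 30% might have absorbed some of it, although the plan assigns it to non-linearity. That also stands. A reader might infer that the omission inflated the 90% by a known or large amount; the documents give no figure that would show it.

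It is also fair to say that what a null SPADI result excludes will be read from the confidence interval of the fitted model, not from planned power, and that with 42 of 44 recruited no recruitment decision turns on this. The value of the correction is that the justification for the reduced size becomes checkable.

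**Conclusion.** The point holds as a failure to support and reconcile the stated powers. Under one variance and one handling of the 15% and 30%, either the 85% is too low (about 95% for 44 patients at 10 points) or the 90% was too high (about 76% for 54 patients at 8 points). The implied variances differ by a factor of 1.49, given a two-sided 5% test, 1:1 allocation and the normal approximation; the one-sided and noncentral t versions barely move it. For the current target, power at 8 points is about 83% or about 67%, depending on which variance applies.

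A reader might infer that the trial is underpowered, or that the sponsor made an arithmetical slip. The documents support neither. Under the first variance the 85% is conservative, and a revised variance or different handling could account for the gap; neither is recorded.

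The statement that the residual variance does not change the power is unsupported. If slopes are compared, leaving it out can only overstate power unless another input already covers it, by an amount that cannot be fixed from the documents. This should be corrected, because the trial relies on the 85% to justify its reduced size.

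**What to change.** - Keep the disclosure that the residual variance was left out, but replace the claim that it does not matter with power over a stated range of residual variances.
- State one set of variance inputs (slope and residual variances, or SD and correlation) with their source, the sidedness of the test, the time horizon of the difference, and how the 15% and the 30% were applied.
- From that set, recompute and restate the power of the 44-patient target (42 recruited by the end of April 2022) at both 8 and 10 points.
- Say whether the variance or the handling of the adjustments was revised after the 54-patient calculation.

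The cost is one recalculation and some reworded text. The downside is that the stated power may become less favourable. No patients, visits, endpoints or tests change.

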#### Physiotherapist and patient recruitment

The physiotherapists participating in the feasibility study agreed in taking part to the second phase of the project (Task 2.1, WP2). They will perform a standardized initial screening of all patients referred with SSP diagnosis. The rate of recruitment estimated in feasibility study will allow us to recruit 54 patients in 1 year time, between April 2020 and April 2021. The last measurement of the last patient should be in October 2021 (6 months follow-up, Task 2.3, WP2). Following the successful procedure developed in the feasibility study, the patient will be screened in two phases: first by the physiotherapist and, if they are willing to participate, secondly by the PhD student at a separate visit.

The **inclusion criteria** are: 1) patients aged 18-65 years old; 2) referred to non-operative physiotherapy treatment due to shoulder pain; 3) shoulder pain for at least three months' duration prior to enrolment; 4) at least three of the following positive provocative shoulder tests: Neer test, Hawkins-Kennedy test, Jobe test, painful arc, external rotation resistance test .

The **exclusion criteria** are: 1) resting pain more than 2/10 on VAS scale; 2) bilateral shoulder pain; 3) history of shoulder surgery, fracture or dislocation; 4) clinically (positive drop-arm test, external or internal rotation lag test) and/or previous ultrasonography examination confirming the presence of full-thickness rotator cuff tear or calcifications larger than 5mm ; 5) evidence of adhesive capsulitis; 6) corticoid injections 6 weeks prior to the study. Further exclusion criteria are: history of cervical or thoracic spine surgery, primary complaint of spinal pain or signs of CNS involvement or signs of cervical nerve root involvement; presence of competing pathologies (inflammatory arthritis, neurological disorders, fibromyalgia, malignancy, psychiatric illness, etc.); primary diagnosis of acromioclavicular pathology, shoulder instability. Furthermore, patients will be excluded if they have a radiologically confirmed fracture, pregnancy or inability to understand spoken and written Dutch.

